
lyophilized powder and is reconstituted with 2 ml of a specific solution to form a homogeneous microbubble suspension. A 0.5 ml bolus of this suspension is administered, followed by a 5 ml saline flush. The arterial phase enhancement process begins immediately after aortic enhancement, lasting for 10 to 30 seconds, followed by the venous phase, which persists for 30 to 120 seconds. Routine archiving of imaging data is performed.

The baseline data of enrolled patients were collected from the electronic medical record system, including the patients' names, genders, hospital admission numbers, examination numbers, puncture dates, and body mass index (BMI). Collect all imaging data (CT, MR, ultrasound, PET, and MRCP, etc.) of the patient on the integrated imaging system, and evaluate and record the imaging characteristics of focal pancreatic lesions. The indicators include the location of the lesion, which is divided into the head, uncinate process, neck, body, and tail; the size of the lesion, measured by the puncture operator and assistant on the maximum cross-section of the lesion displayed on the ultrasound image, with the average value recorded; and the exophytic retrograde morphology of the lesion, assessed by CT or MR. This term refers to the lesion morphology originating from the innermost edge of the pancreas and extending posteriorly beyond the pancreas, or presenting as a perivascular soft tissue sheath surrounding the superior mesenteric artery or celiac trunk, rather than a distinct mass. This is an atypical feature of common pancreatic lesions and is therefore easily overlooked. Information related to pancreatic puncture, including previous puncture history, imaging guidance method, puncture technique, needle gauge, puncture path, auxiliary techniques (contrast-enhanced ultrasound or coaxial technique), operator, post-puncture pathological results, complication status, and repeat puncture status, is collected and recorded by an assistant through the electronic medical record system.

After the puncture, follow-up education is provided to the patient, including a 12-month clinical follow-up. The follow-up encompasses surgical pathology results, repeat puncture pathology results, imaging examination results (CT, MRI, and ultrasound), laboratory test results (complete blood count, liver and kidney function, blood biochemistry, tumor markers, blood and urine amylase), and case records (outpatient and inpatient records).

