The primary endpoint of this study was the inaccuracy of EUS- and US-guided pancreatic biopsy in diagnosing focal pancreatic lesions. Cases were classified as true positive results if the histopathological diagnosis post-biopsy was pancreatic ductal adenocarcinoma (PDAC), pancreatic neuroendocrine tumor (PNET), or other definitive malignant or benign pancreatic tumors, and if these findings were consistent with the results of at least

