12 months of clinical follow-up (including medical history, laboratory tests, imaging studies, and pathological examinations). When post-puncture histopathological diagnosis indicates inflammation or an inconclusive result, further confirmation of the disease nature is required. If the biopsy results suggest inflammation or are inconclusive, but clinical and imaging evidence strongly indicate malignancy, a repeat biopsy or sampling is recommended. The necessity for repeated sample collection is determined through multidisciplinary discussion. For patients without indications for repeat biopsy, at least 12 months of clinical dynamic monitoring is required, including medical history, imaging (CT or MR), and tumor marker tests. Cases where the lesion size remains stable (diameter increase  $\leq 20\%$ ), exhibit imaging characteristics of benign lesions, and show no change in tumor markers are classified as benign. Cases with a diameter increase  $> 20\%$  and an absolute increase of more than 5 mm, along with an increase in tumor markers, are classified as malignant. Based on clinical follow-up of at least 6 months post-procedure, cases ultimately diagnosed as benign were considered true negative results, while those ultimately diagnosed as malignant were considered false negative results. The probability of diagnostic inaccuracy was the percentage of the sum of false positive and false negative cases out of the total number of cases. The secondary study endpoints were the incidence rates of severe complications, mild complications, and repeat biopsy after EUS and US-guided pancreatic biopsy. Post-procedure complications were assessed and graded according to the clinical practice guidelines of the Society of Interventional Radiology. Adverse events related to puncture occurring within 30 days post-operation fall under the category of complications. These include immediate post-puncture bleeding or hematoma, vagal reflex, infection, puncture-related pancreatitis, organ rupture (duodenum or colon), arteriovenous fistula, and arterial dissection.

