Normally distributed measurement data are expressed as mean and standard deviation, while non-normally distributed measurement data are expressed as median and interquartile range (IQR). Categorical data are presented as percentages. For intergroup comparison of normally distributed measurement data, the t-test is used to assess differences; for non-normally distributed data, non-parametric tests are employed. Differences in intergroup categorical data are evaluated using the chi-square test or Fisher's exact test. Missing BMI values, which account for 0-12.7% of all data, are estimated using a random forest-based imputation technique. The propensity score matching (PSM) method was employed to control for confounding factors between the two groups, ensuring a balance of variables across them. PSM utilized a nearest-neighbor 1:1 matching approach with a caliper value set at 0.02. Before and after PSM matching, differences in study endpoints between the EUS-FNA/FNB and US-FNA/CNB groups were compared using chi-square or Fisher's exact tests. In addition to

analyzing the entire population, subgroup analyses were conducted based on lesion size, location, and morphology. A P-value of  $<0.05$  was considered statistically significant. Statistical analysis was conducted using SPSS software (version 26.0; IBM SPSS) and R software (version 4.2.3; R Development Core Team).

All records regarding the identity of enrolled patients are kept confidential and will not be disclosed outside the scope permitted by relevant laws and/or regulations.

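### The primary endpoint divides all errors by all cases, so a difference in malignant share between the EUS and US groups can appear as a difference in accuracy

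*Protocol*

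**What the plan says.** All places are in the section headed Protocol, which is unnumbered.

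- **Endpoint.** The endpoint paragraph states: "The primary endpoint of this study was the inaccuracy of EUS- and US-guided pancreatic biopsy in diagnosing focal pancreatic lesions". It is computed as "the percentage of the sum of false positive and false negative cases out of the total number of cases".
- **True positive.** A biopsy showing PDAC, PNET "or other definitive malignant or benign pancreatic tumors, and if these findings were consistent with the results of at least" 12 months of follow-up counts as a true positive. A confirmed benign tumour is therefore a true positive. False positive is used in the formula but not defined.
- **Negatives.** "When post-puncture histopathological diagnosis indicates inflammation or an inconclusive result, further confirmation of the disease nature is required". Of these, "cases ultimately diagnosed as benign were considered true negative results, while those ultimately diagnosed as malignant were considered false negative results".
- **Comparison.** The statistics paragraph compares the endpoints between the EUS and US groups by chi-square or Fisher's exact test, before and after matching. On matching it says "The propensity score matching (PSM) method was employed to control for confounding factors between the two groups, ensuring a balance of variables across them" and "PSM utilized a nearest-neighbor 1:1 matching approach with a caliper value set at 0.02". It does not name the variables in the score.
- **Other analyses.** The subgroups are lesion size, location and morphology. The secondary endpoints are complications and repeat biopsy. No stated comparison is made by final diagnosis.

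**The concern.** The scoring rules treat the two kinds of lesion unequally. A biopsy that yields only inflammation, or nothing conclusive, is scored correct if the lesion turns out benign and wrong if it turns out malignant. A finally benign lesion can enter the numerator only as a false positive. Most errors therefore come from malignant lesions, while the denominator is every lesion, and the measure depends on the malignant share as well as on how well the biopsy works.

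That matters because guidance route was not randomised. If the EUS and US groups contain different proportions of cancer, part or all of a difference in inaccuracy can reflect which patients were sent to which route. A real difference in missed cancers can also be hidden. The stated analyses would not let a reader tell these situations apart.

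**Working it through.** **Inputs.** The formula and scoring rules come from the endpoint paragraph. The 0.05 significance level comes from the statistics paragraph, which does not state sidedness; two-sided is assumed. The protocol gives no sample size, malignant share, sensitivity or false-positive rate, so there is no figure of its own to reproduce. Every value below is an assumption.

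**Identity.** Let p be the finally malignant share, m the miss rate in malignant lesions (1 − sensitivity) and f the false-positive rate in benign lesions (1 − specificity). Then

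inaccuracy = p·m + (1 − p)·f.

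If both routes have the same m and f, the difference between groups is

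(p₁ − p₂)·(m − f).

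It is zero if p₁ = p₂ or m = f, positive for the group with more cancers if m > f, and reversed if f > m.

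This reads positive as malignant and negative as benign. The protocol's categories do not quite do so, because confirmed benign tumours are true positives and a wrong tumour type has no stated category. The identity is therefore an approximation to the protocol's scoring.

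**Equal performance, no false positives (f = 0).** The last two columns give the chance of P<0.05 from the two-proportion normal approximation, two-sided 5%, equal groups.

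| Sensitivity | Malignant shares | Inaccuracy | 500 per group | 1000 per group |
|---|---|---|---|---|
| 90% | 90% v 85% | 0.90×0.10 = 9.0% v 0.85×0.10 = 8.5% | about 6% | about 7% |
| 90% | 85% v 75% | 0.85×0.10 = 8.5% v 0.75×0.10 = 7.5% | about 9% | about 13% |
| 90% | 90% v 70% | 0.90×0.10 = 9.0% v 0.70×0.10 = 7.0% | about 21% | about 38% |
| 85% | 90% v 70% | 0.90×0.15 = 13.5% v 0.70×0.15 = 10.5% | about 31% | about 54% |

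The nominal rate is 5%.

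**Some false positives.** With m = 15%, f = 2% and shares of 90% v 70%: 0.90×0.15 + 0.10×0.02 = 13.7% against 0.70×0.15 + 0.30×0.02 = 11.1%. The gap falls from 3.0 to 2.6 points.

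**Reversal.** With m = 15%, f = 25% and the same shares: 0.90×0.15 + 0.10×0.25 = 16.0% against 0.70×0.15 + 0.30×0.25 = 18.0%. The group with fewer cancers now looks worse.

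**Masking.** Sensitivities of 90% and 87% with shares of 91% and 70% give 0.91×0.10 = 9.1% and 0.70×0.13 = 9.1%. This case is chosen to cancel exactly. It shows that masking is possible, not that it is likely.

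**After the fix.** In the 85% v 75% case the miss rate in malignant lesions is 10% in both groups. Standardised to the pooled share of 80% (equal groups), inaccuracy is 0.80×0.10 = 8.0% in both, and the artefact disappears.

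**The case against.** Overall inaccuracy is a legitimate summary, and the Objective section asks for a comparison of exactly that measure. A reader might infer that the study's real question is which route misses more cancers, and that the endpoint is therefore the wrong one. The documents do not say so, and that reading is not supported.

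A reader might also infer that the group with more cancers will look less accurate in this study. That needs two conditions the documents do not establish: malignant shares that differ between the compared groups, and a miss rate above the false-positive rate. The scoring rules make the second likely. The first is unknown.

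Matching could remove much of the imbalance. The data paragraph records sex, BMI, previous puncture history and extensive imaging as well as lesion features such as location ("The indicators include the location of the lesion, which is divided into the head, uncinate process, neck, body, and tail"), size and morphology. Any of these may enter the score, and the list of matching variables may properly stand in an SAP that is not available here. This stands: its absence from the protocol is not a fault, and one cannot say that matching fails. But final diagnosis is known only after biopsy and follow-up, so it cannot itself be a baseline matching variable, and the planned pre-matching comparison has no protection at all.

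A 20-point gap in malignant share would also be severe for matched groups. At a 5-point gap and 90% sensitivity the rejection rate is close to nominal. That stands too, and limits how strongly the point can be put.

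**Conclusion.** The point holds in conditional form. As defined and scored, the primary endpoint moves with the malignant share, and the protocol compares it between non-randomised groups without any stated comparison by final diagnosis. When the shares differ and misses are more frequent than false positives, the group with more cancers shows higher inaccuracy at equal sensitivity and specificity. The effect vanishes if the shares or the two error rates are equal, and reverses if false positives are the more frequent.

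The algebra is certain, subject to the undefined false-positive category. The size in this study is unknown. At 90% sensitivity and no false positives, it ranges from 0.5 points with little excess in significant results (shares 5 points apart) to 2.0 points and a 21% to 38% chance of significance (shares 20 points apart, 500 to 1000 per group). This is a reason to add a supportive analysis and to limit the wording of conclusions. It is not a reason to abandon the endpoint.

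**What to change.** 1. Keep overall inaccuracy as the primary endpoint.
2. Define false positive, including how a definitive diagnosis of the wrong tumour type is scored.
3. As a supportive analysis, report by route:
   - the finally malignant share, before and after matching;
   - the miss rate among finally malignant lesions and the error rate among finally benign lesions, each as a risk difference with a 95% confidence interval, adjusted for the matching covariates because subsetting by final diagnosis breaks the pairs;
   - inaccuracy standardised to the pooled malignant share.
4. State that a difference in inaccuracy will be attributed to the guidance route only if the standardised figure and the miss rate in malignant lesions point the same way.

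**Cost.** A few lines of text, using cases already classified. The denominators are smaller, and the benign stratum may be imprecise: with a malignant share of 90% it would be 50 of 500. Final diagnosis is a post-biopsy variable, so matched balance is not guaranteed within strata. Miss rates can also vary with tumour type, size and site, so stratifying reduces the case-mix problem but does not fully isolate the effect of guidance.

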### **Objective**

It is proposed to conduct a retrospective, multicenter, propensity score-matched study to compare the differences in diagnostic inaccuracy, complication rates, and the risk of repeat biopsy between EUS and US-guided pancreatic biopsy techniques for focal pancreatic diseases.

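### After matching, the endpoints are compared only by an unadjusted two-by-two test and matching is said to ensure balance, so any covariate imbalance left over passes into the EUS-US difference

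*Protocol*

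**What the plan says.** The Objective section describes a "retrospective, multicenter, propensity score-matched study to compare the differences in diagnostic inaccuracy, complication rates, and the risk of repeat biopsy". Route was not randomised, so the comparison depends on how confounding is handled.

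The statistical paragraph at the end of the Protocol section names one method for this, propensity score matching, used "to control for confounding factors between the two groups, ensuring a balance of variables across them". On the algorithm it says that "PSM utilized a nearest-neighbor 1:1 matching approach with a caliper value set at 0.02". It does not give the scale of the caliper. The endpoint analysis is then fixed: before and after matching, "differences in study endpoints between the EUS-FNA/FNB and US-FNA/CNB groups were compared using chi-square or Fisher's exact tests". No covariate enters that comparison.

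The primary endpoint is binary: "The probability of diagnostic inaccuracy was the percentage of the sum of false positive and false negative cases out of the total number of cases".

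According to the data-collection paragraph of the same section, gender, BMI, lesion location (five sites), lesion size and exophytic retrograde morphology are recorded. The statistical paragraph also plans subgroup analyses by size, location and morphology.

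**The concern.** Nearest-neighbour matching within a caliper brings paired scores close together. Balance on each covariate follows only if the score model is right, and even then only up to chance in the matched sample. It is something to check, not a property that the method confers.

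Because the endpoint test takes no covariates, imbalance that survives matching goes straight into the EUS-US difference. The subgroup analyses do not repair this, since they report results within strata and leave the overall estimate as it was. The variables needed for a correction are already on file.

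What is at stake is bias in the main comparison and, when there is no true difference, a false-positive rate above the stated 0.05.

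**Working it through.** The protocol gives no number of pairs, event rate, covariate effect or score specification, so there is no figure of its own to reproduce. Both calculations below rest on assumed inputs. From the protocol they take the 1:1 nearest-neighbour match, the 0.02 caliper, the unadjusted test of a binary endpoint and the 0.05 level (assumed two-sided).

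**1. A given imbalance remains on one factor, with no true difference between routes**

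Assumed: a binary prognostic factor with overall prevalence 0.40; inaccuracy p0 without the factor of 5% or 10%; factor odds ratio (OR) of 2 or 3; residual standardised difference (SMD) of 0.1 or 0.2; 300 to 1000 patients per arm.

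- Inaccuracy with the factor: p1 = o/(1 + o), where o = OR × p0/(1 − p0).
- Difference in factor prevalence between arms: d = SMD × √(0.40 × 0.60) = SMD × 0.490.
- Spurious risk difference: d × (p1 − p0).
- Type I error: normal approximation for two independent proportions, centred on the spurious difference.

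Lowest case at SMD 0.2: p0 = 5%, OR 2, o = 0.1053, p1 = 9.52%; 0.098 × 4.52 = 0.44 points. Highest case: p0 = 10%, OR 3, o = 0.333, p1 = 25%; 0.098 × 15 = 1.47 points.

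| p0 | OR | shift, SMD 0.1 (points) | type I error | shift, SMD 0.2 (points) | type I error |
|---|---|---|---|---|---|
| 5% | 2 | 0.22 | 0.051–0.054 | 0.44 | 0.055–0.068 |
| 5% | 3 | 0.42 | 0.054–0.063 | 0.85 | 0.066–0.104 |
| 10% | 2 | 0.40 | 0.052–0.058 | 0.80 | 0.060–0.083 |
| 10% | 3 | 0.73 | 0.057–0.073 | 1.47 | 0.078–0.146 |

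Each type I error range runs from 300 to 1000 per arm.

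**2. What matching would leave in a favourable case**

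Simulation with no route effect, 300 runs per size, 600 or 1500 patients before matching. Route depends on size, location, morphology and BMI; the outcome depends on size, location and morphology. The score contains all four in the correct form. Matching is 1:1 without replacement, with the 0.02 caliper on the probability scale. The unadjusted matched difference is set against the standardised difference from a logistic model with the four covariates.

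| | 600 patients | 1500 patients |
|---|---|---|
| Mean number of pairs | 203 | 514 |
| Mean crude difference before matching (points) | 4.61 | 4.66 |
| Mean unadjusted difference after matching (points) | 0.21 | −0.05 |
| Runs with largest SMD above 0.1 | 6.7% | 0% |
| Mean absolute shift from adjustment (points) | 0.19 | 0.10 |
| 95th percentile of that shift (points) | 0.55 | 0.29 |
| SD of the unadjusted difference (points) | 3.12 | 2.13 |

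In this case matching removes nearly all of the crude difference, and what remains has no evident direction. The typical shift is about 0.06 of a standard deviation (0.19/3.12) with 203 pairs and 0.05 (0.10/2.13) with 514.

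**3. How large a model the data can carry**

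With 100 pairs and 10% inaccuracy (assumed) there are 200 × 0.10 = 20 events. Route, size, five-level location (4 terms), morphology and BMI need 1 + 1 + 4 + 1 + 1 = 8 slopes, or 20/8 = 2.5 events per slope. That is too sparse for an ordinary logistic fit.

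**The case against.** **An unadjusted comparison in a matched set is a recognised analysis.** This stands. With a correct score and a tight caliper it does well, as the second calculation shows. Regression on top is then a safeguard with a modest yield. But the protocol does not give the score covariates or the caliper scale, so a reader cannot take the favourable case as given.

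**Balance diagnostics are commonly left to a statistical analysis plan, and the wording on balance may only state the purpose of matching.** Also fair: the absence of a threshold would not be a finding by itself. The unadjusted endpoint test, however, is fixed in the protocol, and nothing else there corrects the overall estimate.

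**A reader might infer that balance is to be judged by significance tests**, because for continuous variables "the t-test is used to assess differences; for non-normally distributed data, non-parametric tests are employed". The document does not support this. Those sentences are general, come before matching is mentioned, and are not tied to the matched sample.

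**A reader might also take the largest imbalance that escapes P<0.05 as the expected one.** That bound is t × √(2/n), about 0.28, 0.20 and 0.14 SD for 100, 200 and 400 pairs. At 10% inaccuracy and an odds ratio of 2 per SD (assumed), 0.28 SD would move one arm by 1.9 points. The arithmetic is right, but it is a worst case that ignores the caliper and presumes a check the protocol does not prescribe.

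**A full covariate model may be too sparse.** This stands, for the primary endpoint as well as for rare complications, and it limits the fix.

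**Conclusion.** The point holds in a limited form. The protocol presents matching as ensuring balance and fixes an unadjusted test as the only comparison of endpoints after matching. Residual imbalance in covariates already recorded would therefore pass into the EUS-US difference.

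The document does not allow the size to be derived. On the assumptions shown, it is about 0.1 to 0.2 percentage points on average, in absolute value, when the score is right and the caliper is on the probability scale. It is about 0.4 to 1.5 points, with type I error of 0.055 to 0.146, if an SMD of 0.2 remains on a prognostic factor.

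This does not show that the matched result is materially biased, and such a reading would go beyond the text. It is a change worth making because it is cheap and guards against a misspecified score.

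**What to change.** - **Balance.** Replace the statement that matching ensures balance with a check: absolute standardised difference after matching below 0.1 for each covariate. If this is exceeded, re-specify the score and re-match without looking at outcomes.
- **Estimate.** Estimate the matched EUS-US difference in diagnostic inaccuracy from a logistic model with route and the main pre-biopsy prognostic covariates: lesion size, location collapsed to few levels, morphology and BMI. Report it as a standardised risk difference with 95% CI, and keep the chi-square or Fisher's exact test alongside.
- **Model size.** Limit the covariates to what the number of events supports. Where events are few, adjust for the score alone or use penalised (Firth) estimation. This applies to the primary endpoint as well as to rare complications.

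The cost is a change of wording and a little more analysis in R, which the protocol already names. No new data are needed. The drawbacks are some dependence on the outcome model and the fact that unmeasured confounding is not removed.

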### **Background**

The acquisition of pancreatic tissue is a critical step in the diagnosis and treatment of pancreatic diseases and has been included in several international guidelines for pancreatic disease management. Commonly used techniques include open or laparoscopic biopsy, image-guided percutaneous biopsy, and endoscopic ultrasound-guided biopsy. It is essential to establish a pathological diagnosis of the tumor before initiating non-surgical or neoadjuvant therapy. Currently, endoscopic ultrasound (EUS) and ultrasound (US)-guided pancreatic biopsies are recommended as first-line methods for obtaining samples from focal pancreatic lesions. Both methods demonstrate excellent diagnostic performance and are associated with a low incidence of adverse events. EUS-guided pancreatic biopsy, including fine needle aspiration (FNA) and fine needle biopsy (FNB), has become the preferred technique due to its high patient tolerance and low risk of complications. In contrast, image-guided percutaneous biopsy techniques, such as FNA or core needle biopsy (CNB), can obtain more histological specimens for molecular biological testing and genetic testing. Currently, there are no randomized controlled trials directly comparing the effectiveness and safety of these two methods, and most of the previous related studies are single-center, retrospective studies with low evidence strength. Therefore, it is imperative to conduct large-scale, multicenter clinical studies to provide high-quality evidence for the clinical application of both techniques, thereby offering a research basis for formulating individualized pancreatic biopsy protocols.

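### The planned subgroup comparisons by lesion size, location and morphology include no test of whether the EUS-versus-US difference varies between strata, so chance patterns could be read as effect modification

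*Protocol*

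**What the plan says.** All of this stands in the last, statistical part of the section headed Protocol, unless another place is named.

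- **Matching.** One match is described: "PSM utilized a nearest-neighbor 1:1 matching approach with a caliper value set at 0.02". Neither exact matching on a subgroup factor nor rematching within a subgroup is mentioned.
- **Tests.** Endpoints in the two groups, before and after matching, "were compared using chi-square or Fisher's exact tests".
- **Subgroups.** Besides the whole-population analysis, "subgroup analyses were conducted based on lesion size, location, and morphology". The text does not say whether the subgroups use the matched set, the unmatched cohort or sets rematched within subgroup.
- **Threshold.** "A P-value of $<0.05$ was considered statistically significant", with no distinction between whole-population and subgroup results.
- **Factors.** The description of data collection in the same section records location, "which is divided into the head, uncinate process, neck, body, and tail", and "the exophytic retrograde morphology of the lesion, assessed by CT or MR". No size cut point is given, and possible pooling of locations is not addressed.
- **Purpose.** The Background closes with the aim of "offering a research basis for formulating individualized pancreatic biopsy protocols".

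No interaction test is named anywhere.

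**The concern.** A subgroup analysis asks whether the difference between routes depends on the kind of lesion. Separate tests within strata do not answer that. Each asks only whether the routes differ in that stratum, and the result depends on the stratum's size and event count as much as on the effect. A significant result for one lesion type and a non-significant one for another is therefore compatible with the same effect in both.

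A second matter is confounding. This is a retrospective comparison in which matching is meant to make the two groups comparable. Balance over the whole matched set does not show balance within, say, head lesions or small lesions. If the reasons for choosing a route differ between lesion types, a propensity model without those differences can balance the total and leave opposite imbalances in the strata.

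At stake is a conclusion that one route suits certain lesions, drawn from chance or residual confounding.

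**Working it through.** The protocol gives no sample size, event rate or subgroup error rate, so there is no figure of its own to reproduce. The checks below show how the stated method behaves. From the protocol come the three factors, five recorded location levels, one primary and three secondary endpoints, alpha 0.05 and the caliper of 0.02. Everything else is an assumption and is marked so. Tests are taken as two-sided.

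**1. Same true effect in two equal strata: how often is exactly one significant?**

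If overall power is P, the expected test statistic is 1.96 + z(P) overall and t = (1.96 + z(P))/√2 in each half. Power per half is p = Φ(t − 1.96), the opposite tail being negligible. The chance that exactly one half is significant is 2p(1 − p).

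| Overall power (assumed) | t | p per half | 2p(1 − p) |
|---|---|---|---|
| 50% | 1.386 | 0.283 | 0.406 |
| 80% | 1.981 | 0.508 | 0.500 |
| 90% | 2.292 | 0.630 | 0.466 |
| 95% | 2.549 | 0.722 | 0.401 |

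A concrete case, with assumed rates of 15% and 9% and 225 patients per arm in each half:

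- SE = √[(0.15 × 0.85 + 0.09 × 0.91)/225] = 0.0305
- 0.06/0.0305 = 1.967, so power per half is Φ(1.967 − 1.96) ≈ 0.503
- exactly one half significant: 2 × 0.503 × 0.497 ≈ 0.50

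**2. No true difference: chance of at least one P<0.05 on the primary endpoint**

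The independence formula is 1 − 0.95^k for k strata. Because the same patients recur across the three factors, the tests are correlated, so a null simulation was also run (assumed 600 patients, 15% event rate, about equal groups).

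| Assumed levels (size + location + morphology) | k | Independent | Simulated |
|---|---|---|---|
| 2 + 2 + 2 | 6 | 26.5% | 22% |
| 2 + 5 + 2 | 9 | 37.0% | 33% |
| 3 + 5 + 2 | 10 | 40.1% | 36% |

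Over all four endpoints, independence gives 71% to 87%. For 9 strata, 36 tests give 1 − 0.95^36 = 84%. These are upper guides only.

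**3. One interaction test per factor**

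Three tests on the primary endpoint give 1 − 0.95^3 = 14.3% as the nominal chance of any false signal. Each factor's false claim of effect modification is held at 5%.

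**4. Balance within subgroups after one match**

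Simulated 1:1 nearest-neighbour matching, caliper 0.02, 1,500 patients, one binary subgroup factor included as a main effect in the propensity model (all but the ratio, method and caliper assumed):

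- If selection of the route works the same way in both strata, mean standardised differences are about 0 overall and within strata.
- If a covariate's influence on the choice of route differs between strata (log-odds ±0.3 per SD) and the model omits this, the overall difference is 0.003, but the strata show +0.27 and −0.25.

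Discordant pairs are a separate matter. In a simulation of 1,200 patients, 41% to 50% of pairs straddled a 50/50 factor, yet the matched groups differed by no more than 0.01 in the share of patients in each stratum. Pairs that straddle strata do not in themselves unbalance the groups.

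**The case against.** **This is ordinary SAP content.** An SAP may exist that names an interaction test, a size cut point and the analysis set. This stands for the cut point and the analysis set, which are missing detail only. It carries less weight for the method, because the protocol already fixes the tests, matching ratio, caliper, imputation and significance threshold. What those provide for subgroups cannot show that strata differ.

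**The protocol announces no subgroup claim.** The Objective lists only overall differences, and the Background speaks of individualised protocols for the research as a whole. That is correct. A reader might infer that the subgroups are meant to drive individualised choice of route, since no other planned analysis could show that a route suits particular lesions. The link is plausible, but the document does not make it.

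**Splitting the matched set breaks pairs.** A reader might infer that the whole-cohort matched set will be split, and that the comparison then fails because partners land in different strata. The documents do not support the first step, as the analysis set is not stated. The second is wrong. Chi-square and Fisher tests ignore pairing, and an adequate propensity model that includes the factor balances the strata in expectation even when pairs are discordant. The risk that remains is a route-selection pattern that differs across strata and is absent from the model.

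**The magnitudes are assumed.** This is true. The 50% is also the maximum of 2p(1 − p), which is why a range is given. The 84% over 36 tests assumes independence and should not be quoted as the error rate.

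**Conclusion.** The point holds in a limited form. On its natural reading the protocol applies chi-square or Fisher tests within strata at P<0.05 and names no test of whether the difference between routes varies. A split verdict between two equal strata then arises in 40% to 50% of studies under a constant effect, for overall power of 50% to 95%. With no effect, at least one nominally significant stratum on the primary endpoint arises in about 22% to 36%, for 6 to 10 strata. These figures rest on assumed levels, rates and sample size.

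Balance within subgroups is not assured by the one match described. That is weaker than saying that it fails: failure needs selection of the route to work differently across strata in a way that the propensity model misses.

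The whole-population comparison is unaffected. Subgroup results would mislead only if used to claim that the effect differs by lesion type, for instance in support of individualised protocols. The correction is worth making because it is cheap and needs no new patients.

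**What to change.** - For each of size, location and morphology, test the route-by-factor interaction on the primary endpoint in one model, for example logistic regression. Claim a subgroup difference only on that test.
- State the subgroup analysis set. Check covariate balance within each subgroup, and rematch within it, or match exactly on the factor, where balance fails.
- Report subgroup estimates with 95% confidence intervals, not a list of P-values.
- Label subgroup results on the three secondary endpoints exploratory.
- For completeness, state the size cut point and any pooling of locations.

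The cost is a few sentences and a little more analysis of data already held. Interaction tests have low power, so fewer subgroup claims will be possible and a true difference between strata may be missed. Rematching or exact matching may lose some pairs.
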